Précis	A total of 700 subjects will be enrolled. To measure the incidence of contrast-induced nephropathy (CIN), subjects (n = 600) with suspected pulmonary embolism (PE) will be prospectively randomized to CT of the pulmonary arteries (CTPA, iodinated contrast media exposure) or to ventilation-perfusion scintigraphy (VQ, unexposed control). To validate a risk-stratification tool for AKI, alone and in combination with acute-phase markers of renal dysfunction (Cystatin-C and NGAL) in both the exposure and unexposed controls, as well as, an additional non-randomized 100 subjects who will undergo CTPA for suspected PE. All subjects will be followed for the development of acute kidney injury (AKI) occurring ≥ 48 hours and ≤ 168 hours following imaging and subsequent long-term outcomes.
Primary Study Objective	Compare the incidence of acute kidney injury (AKI) consistent with contrast-induced nephropathy (CIN) in 600 patients with suspected PE and an AKIrisk Score ≥ 2 , randomized to CTPA (contrast media exposure) or VQ (unexposed control) imaging.
Secondary Study Objectives	
 1) Validate the AKIRisk score, alone and in combination with acute-phase markers of renal dysfunction (Cystatin-C and/or NGAL), to inform imaging strategies and reduce the risk of CIN. 2) Compare the incidence of AKI and subsequent severe health outcomes in patients exposed to iodinated contrast media and unexposed controls at 30-days and 1-year. 3) Measure the 30-day and 1-year incidence of VTE and subsequent severe health outcomes including outcomes related to VTE and VTE treatment
Safety Objectives	Compare the safety outcomes in both the CTPA and VQ groups including outcomes associated with imaging type, VTE (diagnosed and missed), and treatment of VTE occurring within 7 days of enrollment study imaging.
Primary Endpoint	AKI consistent with CIN, defined as an increase in creatinine $\geq 25\%$ of baseline or an absolute increase in creatinine to ≥ 0.5 mg/dL ≥ 48 hours and ≤ 168 hours of the enrollment PE imaging study.

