Venous Thromboembolism (VTE) including PE and/or DVT will be defined by the identification of one or more thrombus, requiring medical or surgical intervention, in the deep veins of the extremities or in the pulmonary vasculature as determined by ultrasonography, echocardiography, CT, MRI, VQ or on autopsy. We will also record and report severe outcomes secondary to VTE and treatment of VTE, including hemorrhage from anticoagulant treatment.

Complications of PE imaging will be defined for the first 24 hours after imaging, patients will be followed for one or more of the following recorded in the EMR, and requiring medical or surgical intervention: hypotension defined as a SBP ≤90 mmHg or ≥10% below baseline, dyspnea, acute pulmonary edema or hypervolemia, oral swelling, rash or puritis, abdominal pain, nausea or vomiting, altered mental status, or soft tissue contrast media or radio-isotope extravasation. The PI has previously published these methods of outcome determination.⁵³

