Severe Health Outcomes will be defined for each follow-up period (24 hours, 2-7 days, 30 days, and 1 year) as the combined outcome of death from any cause, renal failure, acute myocardial infarction, stroke, and/or one or more symptomatic complications of arterial-vascular disease, in any distribution, (cerebral, coronary, mesenteric, renal or peripheral) requiring surgical or medical therapy.²⁸ Renal failure will be defined by the AKIN 3 criteria: an increase in creatinine 3 times baseline, or a decrease in eGFR_{Scr} $\geq 75\%$, or an absolute increase in creatinine to ≥ 4.0 mg/dL as a result of an increase of at least 0.5 mg/dL, or the need for renal replacement therapy.⁹⁰ The highest recorded creatinine recorded in the EMR during the follow-up period will be used to determine this outcome. Myocardial infarction will be defined as a cardiac catheterization, autopsy or cardiac imaging study demonstrating acute coronary thrombus or non-viable myocardium; or at least one measured troponin I above the 99th percentile and clinical findings consistent with ischemia; or diagnostic ECG findings including acute ST-T changes, new left bundle branch block, or new pathologic Q-waves.^{96,97} Stroke will be defined as an acute, focal neurologic deficit with symptoms lasting longer than 24 hours and/or imaging or autopsy evidence of acute cerebral infarction. Finally, coronary or cerebrovascular events not meeting the criteria for acute myocardial infarction or stroke, including acute coronary syndromes and transient ischemic attack (TIA), are included within the definition of other arterial vascular events if these events required medical or surgical invention. The PI has successfully applied the same methods of outcome determination in a comparable study.^{7,11,20}

Outcomes involving death will be classified by adjudicators as: 1) Renal injury as a significant contributor defined as obvious evidence of renal failure defined by worsening azotemia with complications of renal failure including oliguria, pulmonary edema, hyperkalemia, pericardial effusion, or the need to initiate renal replacement therapy before death; 2) Death from VTE and/or hemorrhage requiring intervention following anticoagulant treatment for VTE; or 3) Unrelated to VTE or Renal injury. Death outcomes 1) and 2) may be identified concurrently.

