5.2 Safety measurements

The study manager will monitor for occurrences of one or more of the following events occurring within 7 days (168 hours) of the enrollment PE imaging study:

- 1) Time to treatment of PE >8 hours defined as the time from study enrollment until initiation of anticoagulant therapy for PE.
- 2) Complications of PE imaging defined as one or more of the following occurring within 24 hours of the enrollment imaging study and requiring medical or surgical intervention: hypotension, difficulty breathing, acute pulmonary edema or hypervolemia, oral swelling, rash or puritis, abdominal pain, nausea or vomiting, altered mental status, or soft tissue contrast media or radio-isotope extravasation.
- 3) Severe health outcomes defined as one or more of the following occurring within 168 hours of the enrollment imaging study: AKI (Acute Kidney Injury Network [AKIN] 1-3); Death (any cause), renal failure, or one or more of the following requiring medical or surgical intervention: acute myocardial infarction, stroke and/or other acute arterial vascular event, in any anatomic distribution, requiring medical or surgical intervention; death with renal injury as a significant contributor defined as obvious evidence of renal failure defined by worsening azotemia with complications of renal failure including oliguria, pulmonary edema, hyperkalemia, pericardial effusion, or the need to initiate renal replacement therapy before death; identification of a venous thromboembolism (VTE, PE and/or DVT) requiring medical or surgical intervention; death from VTE and/or hemorrhage requiring medical or surgical intervention as a result of treatment for VTE.

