- DSMB Recommendations: The lead investigators must arrange for a summary of board recommendations to be sent to each participating IRB. The recommendations are also sent to the study manager, NHLBI, and the clinical investigators.
- Action plan: If the DSMB's recommendations require significant changes or follow-up, NHLBI staff, in collaboration with the study manager, will prepare an action plan outlining the steps required to implement the recommendations.

7. Reports to the DSMB

For each meeting, the study manger with input from NHLBI staff, will prepare summary reports and tables to facilitate the oversight role of the DSMB. The DSMB should discuss at the first or subsequent meetings what data they wish to review and how it should be presented.

8. Statistical Monitoring Guidelines

At the first meeting, review of the protocol will include review of the statistical analysis plan. The DSMB should discuss the adequacy of that plan. The DSMB should discuss the statistical monitoring procedures they propose to follow to guide their recommendations about termination or continuation of the trial. These procedures could include guidelines for early termination for benefit, termination for futility, and termination for safety reasons.

The DSMB can choose to recommend stopping the trial early for evidence of HARM or FUTILITY. A recommendation to stop for HARM would occur if an interim analysis showed strong evidence that the rate of delayed or missed cardiopulmonary SAEs is excessive in the interventional group. The final decision for stopping criteria will be made by the DSMB under advice by its lead statistician. As a general rule, it will be recommended that the DSMB biostatistician use the Lan and DeMets alpha-spending approach to early stopping, a generalization of the O'Brien-Fleming stopping rule adapted to interim analyses where the cumulative sample size is not known until the time of analysis. Briefly, the strategy will require extremely strong evidence of harm (or, equivalently, a very large critical value) at early analyses before making a recommendation to stop the trial. As more outcomes accrue, the stopping boundary will decrease, finally approaching the traditional value corresponding to a p-value of 0.05.

REFERENCES

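### The 7-day safety composite counts PE or DVT found by the index work-up as a severe outcome, so it partly measures detection yield; section 2.2 uses the same name for a different list.

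*Combined protocol and SAP*

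**What the plan says.** Section 5.2, item 3, sets the window and list of the safety composite: "Severe health outcomes defined as one or more of the following occurring within 168 hours of the enrollment imaging study". One component is "identification of a venous thromboembolism (VTE, PE and/or DVT) requiring medical or surgical intervention". The list also holds AKIN stages 1 to 3, death, renal failure, myocardial infarction, stroke and other arterial events, death from VTE, and hemorrhage from VTE treatment. The Safety Endpoints in the Précis use the same wording.

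The Safety Objectives in the Précis cover "VTE (diagnosed and missed), and treatment of VTE occurring within 7 days of enrollment study imaging". Section 2.2 accepts VTE "as determined by ultrasonography, echocardiography, CT, MRI, VQ or on autopsy", which includes both index tests.

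Section 2.2 also has its own definition of Severe Health Outcomes, applied at 24 hours, 2 to 7 days, 30 days and 1 year. It reads in part: "as the combined outcome of death from any cause, renal failure, acute myocardial infarction, stroke, and/or one or more symptomatic complications of arterial-vascular disease". Renal failure there means AKIN 3. VTE has its own definition in the same section.

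**The concern.** The trial compares two imaging tests for PE. For a patient who has PE, a positive scan is the test doing its job. The composite scores that patient as a severe outcome as soon as the PE needs treatment. A patient whose PE is missed scores only if it is identified by day 7, or if it leads to another listed event such as death. A between-arm difference can therefore reflect how much VTE each pathway finds, and a less sensitive pathway can appear safer.

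The naming adds to this. A table headed *severe health outcomes* could follow either list, and the two lists give different counts in the first week.

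**Working it through.** **Inputs.**
- 300 patients per randomized arm (section 2.1).
- PE on the index study: 8% CTPA, 10% VQ, 100 patients each (section 1.5, Table 3). Exact 95% intervals reproduce the table: 8/100 gives 3.5 to 15.2% (stated 4 to 15), and 10/100 gives 4.9 to 17.6% (stated 5 to 18).
- 45-day VTE incidence of 3% at pre-test risk 2.5 to 20% (section 1.5). This is not an index-scan rate and is used only as a low-end assumption.
- The plan states no expected rate for this composite, so there is no figure of its own to reproduce. The rate of all other components, h, is assumed. The range 6 to 32% borrows the two AKI rates in Table 3, and 20% is used for illustration.

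**Patients scored because VTE was found.** 300 × 3% = 9; 300 × 8% = 24; 300 × 10% = 30 per arm, taking every such VTE as needing treatment.

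**Share of the composite.** With v the VTE rate, all found, and independent of the other components, the composite is 1 − (1 − h)(1 − v). The part due to VTE alone is v(1 − h).
- h = 32%, v = 3%: 0.0204 / 0.3404 = 6%.
- h = 6%, v = 10%: 0.094 / 0.154 = 61%.

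**Effect of missing PE.** Let d be the share of true PE identified by day 7. The composite is 1 − (1 − h)(1 − v·d). Take v = 8% and h = 20% in both arms, with one test finding all PE and the other missing 2 of 8.

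| Missed PE surfacing by day 7 | Full detection | Misses 2 of 8 | Apparent advantage of the less sensitive test |
|---|---|---|---|
| None (d = 0.75) | 1 − 0.8 × 0.92 = 26.4% | 1 − 0.8 × 0.94 = 24.8% | 1.6 points |
| Half (d = 0.875) | 26.4% | 1 − 0.8 × 0.93 = 25.6% | 0.8 points |
| All (d = 1) | 26.4% | 26.4% | 0 |

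With no overlap with other events the first row becomes 8% × 2/8 = 2.0 points, the ceiling for this scenario. If instead the second test finds 80% of PE and no missed PE surfaces, the advantage runs from 0.4 points (v = 3%, h = 32%) to 1.9 points (v = 10%, h = 6%).

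**Same scenario with index VTE not counted.** The fully detecting test gives 20.0%. The test that misses 2 of 8 gives 20.0%, 1 − 0.8 × 0.99 = 20.8%, or 1 − 0.8 × 0.98 = 21.6% when none, half or all of its misses surface. The false advantage disappears, and any remaining difference points the right way.

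**The two lists side by side.**

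| Component | Précis and 5.2 (0 to 168 hours) | 2.2 (24 hours, 2 to 7 days, 30 days, 1 year) |
|---|---|---|
| Death, MI, stroke, arterial events | yes | yes |
| Renal failure / AKIN 3 | yes | yes |
| AKIN 1 and 2 | yes | no |
| VTE identified and treated | yes | no (separate outcome) |
| Hemorrhage from VTE treatment | yes | no |

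**The case against.** The safety scope names diagnosed as well as missed VTE, so counting diagnosed VTE may be deliberate. That supports the literal reading of the composite. It does not make yield a harm, and it gives no reason to pool the two.

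A reader might infer that every missed PE counts in a test's favour. The documents do not support that. A missed PE found by day 7 counts like one found on the scan, a fatal one counts as a death, and one treated more than 8 hours after enrollment triggers safety item 1. VTE is also followed at 30 days and 1 year. What escapes is a missed, non-fatal PE not identified by day 7. Safety item 1 does not catch it if it is never treated, and the schedule in section 5.3 lists no routine repeat PE imaging.

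A reader might also infer that the monitoring board's signal on missed disease is reversed. It is not. The charter's harm criterion (section 6.3) is whether "the rate of delayed or missed cardiopulmonary SAEs is excessive in the interventional group", which does not rest on this composite, and the stopping rule in section 6.1 uses AKI only. These are partial offsets, but they leave the composite as it is. The separation of expected events in section 6.2.4 concerns reporting and does not change it either.

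Two further inferences fail. Section 2.2 does not leave out AKI altogether, since AKIN 3 enters through renal failure. And no AKIN 1 to 3 rate is planned; the figure below 20% in section 2.1 is the overall AKI rate assumed for the sample size.

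The 8 to 10% comes from a retrospective sample with median age 73 and median eGFR 37, so the trial's rate may be lower. That is why the range starts at 3%.

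**Conclusion.** The point holds as a fault in a safety definition. No text names the index scan as a source of events. The reading rests on the word identification, the 168-hour window, and the absence of any exclusion. A reading limited to later events is possible but is not written.

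About 9 to 30 patients per arm would score because VTE was found. The false advantage for a less sensitive test is about 1.6 points in the main scenario, 2 at its ceiling, and 0 if all missed PE surface by day 7. These figures depend on the assumed sensitivity, the assumed rate of other events, and independence between components. Which arm would gain is not known: Table 3 shows slightly more PE on VQ, while section 1.7 cites over-diagnosis of small PE in favour of VQ.

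Separately, one term has two component lists over overlapping periods. The primary AKI comparison and the sample size are unaffected. The change should be made.

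**What to change.** 1. In the Précis and section 5.2, limit the VTE component to VTE first identified after a negative index work-up. Keep death from VTE and treatment-related hemorrhage. State what the index work-up includes: the scan, its ultrasound, and whether the crossover CTPA in section 6.0 belongs to it.
2. Report VTE found by the index work-up separately by arm, as diagnostic yield.
3. Use one definition of *severe health outcomes* in the Précis, 2.2 and 5.2, or give the two composites different names. Separate reporting of AKIN 1 to 3 is already planned in section 2.2 and needs no addition.

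The cost is protocol wording, fewer events in the composite, and a record for each VTE of whether it came from the index work-up. The documents do not show that such a field exists, so it may have to be added.

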5.3 Study schedule and benchmarks

Study Events Schedule						
Procedure	Screening/ Enrollment	24 Hours after PE Imaging	≥ 48 hours and ≤168 hours	7-Day Follow-up	30-Day Follow-up	1-Year Follow-Up

			after PE imaging			
Inclusion/Exclusion Review	X					
Informed Consent	X					
Chest Radiograph	X		X			
Urine Sample	X		X			
Blood Sample/Creatinine	X		X			
Interview			X	X (If return visit not completed)		
EMR Review	X	X	X	X	X	X
Assess Primary Outcome			X	X		
Assess Secondary Outcomes		X	X	X	X	X
Asses SAEs		X	X	X		

6.0 Safety Assessment and Reporting

The study coordinators will also communicate closely with the clinical team, inform them of the PE imaging randomization assignment, and assist the clinical team to coordinate the completion of the PE imaging. The study coordinator will notify the treating provider of any conditions that exclude the patient from participation in this study. A study physician will be available by telephone during patient enrollment and the completion of PE imaging. The flowchart shown in appendix 1. describes the study procedures including randomization, assessment of outcomes, and PE imaging completion, including the process for crossover from the VQ arm to CTPA. Patients with suspected DVT will also undergo lower extremity ultrasound (US), at the discretion of the treating provider, as will patients with an intermediate risk VQ. Thus, only patients who, after pre-enrollment screening for non-high risk of PE, appropriateness for VQ imaging, have an intermediate risk VQ study and a negative DVT US, will require crossover to CTPA to exclude PE.

Patients who develop CIN, based on the study definition and follow-up creatinine measurement, will receive a telephone call notifying them of this result. If the patient cannot be reached by telephone, we will also send a letter (paper mail, and if provided, email) informing them of their creatinine measurement. The same notification letter will provide instructions to seek follow-up care with either their primary care physician, or for patients without a primary care physician, with instructions to follow-up in the emergency department.

6.1 Criteria for Discontinuation of Study

If we find that lower limit of 95% confidence interval of the difference in rate of AKI is greater than 15% between groups, we plan to discontinue the study. This will be assessed annually.

6.2 Adverse Events

6.2.1 Definitions

An **adverse event** (AE) is any undesirable medical occurrence or untoward deviation in health from baseline. A **serious adverse event** (SAE) will be defined in accordance with ICH-GCP guidelines (any unexpected illness or injury that poses a threat to life or body function and causes medical or surgical intervention or prolongation of hospitalization). An **unanticipated adverse event** is one that is not identified in nature, severity, or frequency in the current protocol and informed consent document. A **related adverse event or adverse effect** is one that is definitely or probably a result of participation in the study (likely would not have occurred as part of standard care).

6.2.2 Investigator Records

Records and documents pertaining to the conduct of this study, CRF and consent forms will be maintained by the PI for 2 years after the investigation is discontinued. The study binder will contain information including IRB approval letters, documentation of GCP training, human subjects research ethics training certificates, curriculum vitae, and correspondence.

6.2.3 Follow-up Procedure

Safety assessments will consist of monitoring, using the methods previously defined, and reporting serious adverse events (SAEs) that could be considered unanticipated and related to study participation in accordance with CFR 312.32 (IND Safety Reports). CRFs will be inspected periodically and compare them with certified source documents. In addition to the original medical record, the study will employ a data collection template as a source document. This form contains the data fields that historically have been difficult to abstract from the medical record.

6.2.4 Investigator Reports

All serious adverse events (SAEs), related or unrelated to the study, will be reported to the PI and project manager by scanning a copy of the IRB SAE reporting form and attaching to an email addressed to the project manager and PI.

All SAEs occurring within 168 hours of the enrollment imaging study, whether reported by the patient, or discovered from the medical record will be reported. Each SAE will be described by its duration (i.e., start and end dates), regulatory seriousness criteria, and, if applicable, suspected relationship to study participation. In general, these relationships will be categorized as likely, possible, unlikely and not related.

Adverse events (SAEs or AEs) that are known to occur with patients who are evaluated for PE with either CTPA or VQ, and, if identified on imaging, with a VTE (PE and/ or its precursor DVT), will be considered to be anticipated and excluded from reporting to the NIH (but not from internal analysis) unless determined to be serious, unanticipated and related. This information will be assessed quarterly by the Principal Investigator.

The following signs, symptoms, observations and events are frequently observed in association with CTPA and VQ imaging, and with PE and/or DVT, treatment for VTE, or other cardiopulmonary emergencies that will be diagnosed and are exempted from regulatory reporting unless serious, unanticipated and related to the study: hypotension, dyspnea, acute pulmonary edema or hypervolemia, oral swelling, rash or puritis, abdominal pain, nausea or vomiting, altered mental status, or soft tissue injury from contrast media or radio-isotope extravasation, chest pain, fever, hypoxemia, rapid pulse, rapid respiratory rate, dizziness, syncope, altered mental status, seizure, confusion, anxiety, tingling sensations, numbness or pain of limbs, generalized weakness, exertional intolerance, hemoptysis, anorexia, nausea, abdominal pain, back pain, constipation, vomiting, congestive heart failure, angina pectoris, pneumonia, skin infection, limb swelling, cancer, surgery not related to treatment of VTE or hemorrhage, electrocardiography abnormalities (atrial arrhythmias, right bundle branch block, and ST and T wave changes), pulmonary hypertension, pulmonary infiltrate, pleural effusion, cardiomegaly, need for oxygen therapy, need for physical or occupational therapy, and hemorrhage associated with anticoagulant therapy.

Diagnosis vs. Signs and Symptoms: If known at the time of reporting, a diagnosis will be reported rather than individual signs and symptoms. However, if a constellation of signs or symptoms cannot be medically characterized as a single diagnosis or syndrome at the time of reporting, it will not be reported as an SAE. Purely descriptive terms will not be used as the basis of an SAE (e.g., "chest pain, etiology unknown"). If a diagnosis is subsequently established, it will be reported as follow-up information.

Deaths: All deaths that occur during within 7 days, regardless of attribution, will be reported, if required by IRB, using available information regarding causation and relationship.

Preexisting Medical Conditions: A preexisting medical condition is one that is present at the start of the study. Such conditions will be reported as medical and surgical history. A preexisting medical condition will be re-

assessed throughout the trial and reported as an SAE only if the frequency, severity, or character of the condition worsens during the study to the point where it requires intervention to prevent loss of life, limb or organ function.

Hospitalizations for Medical or Surgical Procedures: Any AE that results in hospitalization or prolonged hospitalization will be documented and reported as a SAE. If a subject is hospitalized to undergo a medical or surgical procedure as a result of an AE, the event responsible for the procedure, not the procedure itself, will be reported as the SAE. At follow-up, if the patient indicates he or she had a hospitalization (defined as non-observational stay >24 hours in an acute care facility), the study coordinator will obtain a copy of the discharge summary for each hospitalization and will report, verbatim, on the CRF the discharge diagnoses listed.

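### Section 6.2.4 bars undiagnosed events from SAE reporting even when serious, contradicting the other SAE rules and leaving a gap in the counts behind the DSMB harm criterion

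*Combined protocol and SAP*

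**What the plan says.** The rule in question is the paragraph Diagnosis vs. Signs and Symptoms in section 6.2.4. It opens by preferring a diagnosis to its component symptoms where one is known. It then says of any group of signs or symptoms that, where it "cannot be medically characterized as a single diagnosis or syndrome at the time of reporting, it will not be reported as an SAE". It adds: "Purely descriptive terms will not be used as the basis of an SAE", with chest pain of unknown cause as the example. It closes: "If a diagnosis is subsequently established, it will be reported as follow-up information".

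Four other statements bear on the same events:

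- Section 6.2.1 defines an SAE as "any unexpected illness or injury that poses a threat to life or body function and causes medical or surgical intervention or prolongation of hospitalization".
- Section 6.2.4, opening: "All serious adverse events (SAEs), related or unrelated to the study, will be reported to the PI and project manager".
- Section 6.2.4, next paragraph: "All SAEs occurring within 168 hours of the enrollment imaging study" are to be reported, whether the patient mentions them or the record reveals them.
- Section 6.2.4, hospitalization paragraph: "Any AE that results in hospitalization or prolonged hospitalization will be documented and reported as a SAE".

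Item 8 of the DSMB charter (section 6.3) ties a recommendation to stop for harm to strong interim evidence that "the rate of delayed or missed cardiopulmonary SAEs is excessive in the interventional group".

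**The concern.** Four statements make reporting depend on how serious an event is or what it leads to. One makes it depend on whether the event has a name. Nothing says which prevails, so staff at the five sites could classify the same event differently.

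This matters because the trial compares two ways of looking for pulmonary embolism, and the safety objective in the synopsis covers VTE that is missed as well as diagnosed. Missed disease has no diagnosis at first and may show itself only as symptoms. The harm criterion is expressed in SAEs. A rule that keeps undiagnosed events out of that category can therefore lower the count the criterion uses.

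**Working it through.** No arithmetic applies, and the plan gives no figure to reproduce. The check is whether the rules can be obeyed together and, if not, which events fall between them.

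**Step 1: one event under each rule.** Take a patient whose hospital stay is prolonged on day 3 by collapse with low oxygen that needs treatment, with no diagnosis or syndrome assigned when the report is due.

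- Section 6.2.1: the event threatens life or body function, needs intervention and prolongs the stay. If it is also unexpected, it is an SAE. No diagnosis is required.
- Section 6.2.4, all-SAE rules: day 3 is within 168 hours, so it is reported.
- Section 6.2.4, hospitalization paragraph: it prolonged the stay, so it is reported as an SAE. This is the cleanest conflict, because this paragraph does not ask whether the event was unexpected.
- Section 6.2.4, signs-and-symptoms paragraph: it has no diagnosis or syndrome, so it is not reported as an SAE.

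The last result contradicts the others. The case is realistic: section 4.1 puts admission at about 65% of patients in whom CTPA is ordered.

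**Step 2: is this only a coding convention?** The opening sentence of the paragraph is one, since it tells staff which term to use. The next sentence decides whether a report is made at all. The closing sentence speaks of follow-up information, but under the rule there would be no initial SAE report to follow up.

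**Step 3: what other channels catch.** Section 5.2 monitors the following separately from SAE reporting:

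- through 168 hours: death from any cause, renal failure, AKI, myocardial infarction, stroke and other arterial events, and VTE that is identified and needs intervention;
- PE treatment that starts more than 8 hours after enrollment;
- a list of symptoms, including hypotension, difficulty breathing and altered mental status, but only within 24 hours of imaging and only if intervention is needed. Chest pain and syncope are not on this list.

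Section 6.2.4 also has discharge diagnoses copied to the CRF. Charter item 4 has the DSMB review adverse event and other safety data at each meeting.

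**Step 4: what is left.** The remaining gap is serious cardiopulmonary events without a diagnosis or syndrome, mainly after 24 hours, that do not end in death, an identified VTE or another named endpoint. They may be seen as other data, but they are not counted as SAEs.

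**Step 5: size.** The documents give no rate for such events in either arm, so their number cannot be worked out.

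**The case against.** The best defense is that the paragraph governs a label and not data capture. Much of this stands. The DSMB's remit under charter item 4 is wider than SAEs, and item 7 lets it choose what it reviews. Section 6.2.4 keeps anticipated events in internal analysis even when they are not sent to the NIH. A PE that is missed and later found is reported under the closing sentence of the paragraph and, if identified within 168 hours and treated, counts as a section 5.2 endpoint. Section 2.2 provides for VTE outcomes at 30 days and 1 year, decided by blinded reviewers. The word syndrome also gives sites some latitude.

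Relabeling would also do little for rapid notification. Section 6.2.5 sends an SAE to the DSMB within 24 hours only if it is unanticipated and related. Section 6.2.4 lists dyspnea, chest pain, syncope, hypotension and hypoxemia among events commonly seen in these patients, exempt from regulatory reporting unless serious, unanticipated and related.

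A reader might therefore infer too much: that the rule hides missed PE, or removes these events before the DSMB can see them. The documents do not support that, for the reasons just given. Nor do they show that the omitted events would gather in the VQ arm. The charter does not say which arm it means by the interventional group, and no rate by arm is given. Putting a number on the loss would mean choosing a rate with no basis in the documents.

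None of this removes the contradiction. The harm criterion is still expressed in SAEs, and the exemption list itself accepts that a bare symptom can be a serious, reportable event.

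**Conclusion.** The contradiction is established from the protocol's text alone and needs no assumption about event rates. The signs-and-symptoms paragraph cannot be followed together with the all-SAE rules and the hospitalization rule for a serious event that lacks a diagnosis or syndrome at reporting.

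The consequence is limited but real. If sites follow that paragraph, the SAE counts behind the DSMB harm criterion will omit the residual events identified above. This is undercounting in one category, not loss of all data, and its size is unknown. It assumes that the DSMB counts SAEs as section 6.2.4 classifies them. If the DSMB asks for symptom-level adverse events by arm, the practical effect shrinks. The wording should be corrected; the trial's design is not in question.

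**What to change.** Reconcile section 6.2.1 with the paragraphs of 6.2.4. State that any event meeting the 6.2.1 seriousness definition is reported as an SAE under its signs or symptoms when no diagnosis or syndrome is available, and that the report is updated when a diagnosis is made. Keep the preference for a diagnosis as a rule on terms only. Delete or qualify the sentence on descriptive terms so that it does not block a serious event, and say that the hospitalization rule applies with or without a diagnosis.

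The cost is a protocol wording change and a few more SAE forms. Sample size, procedures and the primary analysis are unaffected.
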